9.0 Ancillary Treatment/Supportive Care

- 9.1 Antiemetics may be used at the discretion of the attending physician.
- 9.2 Blood products and growth factors should be utilized as clinically warranted and following institutional policies and recommendations.
- 9.3 Patients should receive full supportive care while on this study. This includes blood product support, antibiotic treatment, and treatment of other newly diagnosed or concurrent medical conditions. All blood products and concomitant medications such as antidiarrheals, analgesics, and/or antiemetics received from the first day of study treatment administration until 30 days after the final dose will be recorded in the medical records.
- 9.4 **Antifungal antibiotics:** It is highly recommended to avoid concomitant strong CYP3A4 inhibitors (e.g., ketoconazole, itraconazole, voriconazole, posaconazole). The suggested antifungal regimens from a drug metabolism perspective to avoid to use is described below:
Prophylaxis:
Fluconazole (moderate CYP3A4 inhibitor)
Caspofungin

If a patient requires active treatment for a fungal or mold infection and there are no other treatment options it becomes necessary to administer an azole which is a strong CYP3A4 inhibitor. If this is needed, the suggested agents from a drug metabolism and safety perspective include:

Treatment

Voriconazole

Posaconazole

These are both strong CYP3A4 inhibitors and will likely increase midostaurin concentrations, therefore, if there are no other treatment options to treat the infection, a dose reduction by 50% of midostaurin is required to compensate for the drug interactions with these strong CYP3A4 inhibitors. With intra-patient variability with regard to CYP3A4 inhibition and midostaurin pharmacokinetics, the suggested approach is to avoid strong CYP3A4 inhibitors unless there are no treatment alternatives.

- 9.5 Hydroxyurea: Can be used for control of elevated WBC/blasts at any time of treatment for patient best care and avoid complications of hyperleukocytosis.

10.0 Adverse Event (AE) Reporting and Monitoring

10.1 Adverse Event Characteristics

CTCAE term (AE description) and grade: The descriptions and grading scales found in the revised NCI Common Terminology Criteria for Adverse Events (CTCAE) version 4.0 will be utilized for AE reporting. All appropriate treatment areas should have access to a copy of the CTCAE version 4.0. A copy of the CTCAE version 4.0 can be downloaded from the CTEP web [site](http://ctep.cancer.gov/protocolDevelopment/electronic_applications/ctc.htm): (http://ctep.cancer.gov/protocolDevelopment/electronic_applications/ctc.htm)

10.11 Adverse event monitoring and reporting is a routine part of every clinical trial. First, identify and grade the severity of the event using the CTCAE version 4.0. Next, determine whether the event is expected or unexpected (see Section 10.2) and if the adverse event is related to the medical treatment or procedure (see Section 10.3). With this information, determine whether the event must be reported as an expedited report (see Section 10.4). Expedited reports are to be completed within the timeframes and via the mechanisms specified in Sections 10.4. All AEs reported via expedited mechanisms must also be reported via the routine data reporting mechanisms defined by the protocol (see Sections 10.52 and 18.0).

10.12 Each CTCAE term in the current version is a unique representation of a specific event used for medical documentation and scientific analysis and is a single MedDRA Lowest Level Term (LLT).

- **NOTE:** A severe AE, as defined by the above grading scale, is **NOT** the same as serious AE which is defined in the table in Section 10.4.

10.2 Expected vs. Unexpected Events

- The determination of whether an AE is expected is based on agent-specific information provided in Section 15.0 of the protocol.
- Unexpected AEs are those not listed in the agent-specific information provided in Section 15.0 of the protocol.

NOTE: “Unexpected adverse experiences” means any adverse experience that is neither identified in nature, severity, or frequency of risk in the information provided for IRB review nor mentioned in the consent form.

10.3 Assessment of Attribution

When assessing whether an adverse event is related to a medical treatment or procedure, the following attribution categories are utilized:

- Definite - The adverse event *is clearly related* to the agent(s).
- Probable - The adverse event *is likely related* to the agent(s).
- Possible - The adverse event *may be related* to the agent(s).

Unlikely - The adverse event *is doubtfully related* to the agent(s).
Unrelated - The adverse event *is clearly NOT related* to the agent(s).

Events determined to be possibly, probably or definitely attributed to a medical treatment suggest there is evidence to indicate a causal relationship between the drug and the adverse event.

10.31 AEs Experienced Utilizing Investigational Agents and Commercial Agent(s) on the SAME Arm

NOTE: The combination of an investigational agent with a commercial agent is considered investigational.

Routine Reporting

- Routine AE reporting for Phase 1 and Phase 2 clinical studies using an investigational agent /intervention in combination with a commercial agent is stated in the protocol. See Section 10.52.

NOTE: When a commercial agent(s) is (are) used on the same treatment arm as the investigational agent/intervention (also, investigational drug, biologic, cellular product, or other investigational therapy under an IND), the entire combination (arm) is then considered an investigational intervention for reporting.

Expedited Reporting

- An AE that occurs on a combination study must be assessed in accordance with the guidelines for CTEP investigational agents/interventions in Section 10.4, and where indicated, an expedited report must be submitted.
- An AE that occurs prior to administration of the investigational agent/intervention must be assessed as specified in the protocol. In general, only Grade 4 and 5 AEs that are unexpected with at least possible attribution to the commercial agent require an expedited report. Refer to Section 10.4 for specific AE reporting requirements or exceptions.
- Commercial agent expedited reports must be submitted to the FDA via MedWatch.
- An investigational agent/intervention might exacerbate the expected AEs associated with a commercial agent. Therefore, if an expected AE (for the commercial agent) occurs with a higher degree of severity, expedited reporting is required. The clinical investigator must determine severity.

10.32 Special Situations for Expedited Reporting and submission of Notification Forms

Exceptions to Expedited Reporting and Submission of Notification Forms: EXPECTED Serious Adverse Events¹

An expedited report or notification form may not be required for specific Serious Adverse Events where the AE is listed in Section 15.0 of the protocol as **EXPECTED**. Any protocol specific reporting procedures **MUST BE SPECIFIED BELOW** and will supersede the standard Expedited Adverse Event Reporting and Notification Form Requirements (see footnote 1):

System Organ Class (SOC)	Adverse event/ Symptoms	CTCAE Grade at which the event will not be expeditedly reported.
General disorders and administration site conditions	Fatigue Febrile neutropenia	≤Grade 3
Metabolism and nutrition disorders	Hypophosphatemia	≤Grade 3
Blood and lymphatic system disorders	Anemia	≤Grade 4
Investigations	Lymphocyte count decreased	≤Grade 4
	Neutrophil count decreased	≤Grade 4
	Platelet count decreased	≤Grade 4
	White blood cell decreased	≤Grade 4

¹ These exceptions only apply if the adverse event does not result in hospitalization. If the adverse event results in hospitalization, then the standard expedited adverse events reporting requirements must be followed.

Specific protocol exceptions to expedited reporting should be reported expeditiously by investigators **ONLY** if they exceed the expected grade of the event.

10.321 Persistent or Significant Disabilities/Incapacities

Any AE that results in persistent or significant incapacity or substantial disruption of the ability to conduct normal life functions (formerly referred to as disabilities), congenital abnormalities or birth defects, must be reported immediately if they occur at any time following treatment with an agent under an IND/IDE since they are considered to be a serious AE and must be reported to the sponsor as specified in 21 CFR 312.64(b).

10.322 Death

- Any death occurring within 30 days of the last dose, regardless of attribution to an agent/intervention

under an IND/IDE requires expedited reporting within 24-hours.

- Any death occurring greater than 30 days with an attribution of possible, probable, or definite to an agent/intervention under an IND/IDE requires expedited reporting within 24-hours.
- **Reportable categories of Death**
 - Death attributable to a CTCAE term.
 - Death Neonatal: A disorder characterized by cessation of life during the first 28 days of life.
 - Death NOS: A cessation of life that cannot be attributed to a CTCAE term associated with Grade 5.
 - Sudden death NOS: A sudden (defined as instant or within one hour of the onset of symptoms) or an unobserved cessation of life that cannot be attributed to a CTCAE term associated with Grade 5.
 - Death due to progressive disease should be reported as **Grade 5 “Neoplasms benign, malignant and unspecified (including cysts and polyps) – Other (Progressive Disease)”** under the system organ class (SOC) of the same name. Evidence that the death was a manifestation of underlying disease (e.g., radiological changes suggesting tumor growth or progression: clinical deterioration associated with a disease process) should be submitted.

10.323 Secondary Malignancy

- A *secondary malignancy* is a cancer caused by treatment for a previous malignancy (e.g., treatment with investigational agent/intervention, radiation or chemotherapy). A secondary malignancy is not considered a metastasis of the initial neoplasm.
- All secondary malignancies that occur following treatment with an agent under an IND/IDE need to be reported. Three options are available to describe the event:

- Leukemia secondary to oncology chemotherapy (e.g., Acute Myeloid Leukemia [AML])
- Myelodysplastic syndrome (MDS)
- Treatment-related secondary malignancy
- Any malignancy possibly related to cancer treatment (including AML/MDS) should also be reported via the routine reporting mechanisms outlined in each protocol.

10.324 **Second Malignancy**

- A second malignancy is one unrelated to the treatment of a prior malignancy (and is NOT a metastasis from the initial malignancy). Second malignancies require ONLY routine reporting.

10.4 Expedited Reporting Requirements for IND/IDE Agents

10.41 Late Phase 2 and Phase 3 Studies: Expedited Reporting Requirements for Adverse Events that Occur on Studies under an IND/IDE within 30 Days of the Last Administration of the Investigational Agent/Intervention^{1,2}

FDA REPORTING REQUIREMENTS FOR SERIOUS ADVERSE EVENTS (21 CFR Part 312)
NOTE: Investigators **MUST** immediately report to the sponsor **ANY** Serious Adverse Events, whether or not they are considered related to the investigational agent(s)/intervention (21 CFR 312.64)
 An adverse event is considered serious if it results in **ANY** of the following outcomes:

- 1) Death
- 2) A life-threatening adverse event
- 3) An adverse event that results in inpatient hospitalization or prolongation of existing hospitalization for ≥ 24 hours
- 4) A persistent or significant incapacity or substantial disruption of the ability to conduct normal life functions
- 5) A congenital anomaly/birth defect.
- 6) Important Medical Events (IME) that may not result in death, be life threatening, or require hospitalization may be considered serious when, based upon medical judgment, they may jeopardize the patient or subject and may require medical or surgical intervention to prevent one of the outcomes listed in this definition. (FDA, 21 CFR 312.32; ICH E2A and ICH E6).

ALL SERIOUS adverse events that meet the above criteria **MUST** be immediately reported to the sponsor within the timeframes detailed in the table below.

Hospitalization	Grade 1 Timeframes	Grade 2 Timeframes	Grade 3 Timeframes	Grade 4 & 5 Timeframes
Resulting in Hospitalization ≥ 24 hrs	7 Calendar Days			24-Hour 3 Calendar Days
Not resulting in Hospitalization ≥ 24 hrs	Not required		7 Calendar Days	

NOTE: Protocol specific exceptions to expedited reporting of serious adverse events are found in section 10.32 of the protocol.

Expedited AE reporting timelines are defined as:

- o "24-Hour; 3 Calendar Days" - The AE must initially be reported within 24 hours of learning of the AE, followed by a complete expedited report within 3 calendar days of the initial 24-hour report.
- o "7 Calendar Days" - A complete expedited report on the AE must be submitted within 7 calendar days of learning of the AE.

¹Serious adverse events that occur more than 30 days after the last administration of investigational agent/intervention and have an attribution of possible, probable, or definite require reporting as follows:
Expedited 24-hour notification followed by complete report within 3 calendar days for:

- All Grade 4, and Grade 5 AEs

Expedited 7 calendar day reports for:

- Grade 2 adverse events resulting in hospitalization or prolongation of hospitalization
- Grade 3 adverse events

²For studies using PET or SPECT IND agents, the AE reporting period is limited to 10 radioactive half-lives, rounded UP to the nearest whole day, after the agent/intervention was last administered. Footnote "1" above applies after this reporting period.

Effective Date: May 5, 2011

Additional instructions:

Additional Instructions:

1. An increased incidence of an expected adverse event (AE) is based on the patients treated for this study at their site. A list of known/expected AEs is reported in the package insert or the literature, including AEs resulting from a drug overdose.
2. Submit form to the FDA, MedWatch, [name], by fax at [REDACTED] or online at <http://www.fda.gov/Safety/MedWatch/HowToReport/default.htm>.

Mayo Clinic Cancer Center (MCCC) Institutions: Provide copies, along with the UPIRTSO cover sheet, by fax [REDACTED] to the MCCC Regulatory Affairs Unit (RAU) Risk Information Specialist who will determine and complete IRB reporting. The RAU will submit to the MCCC SAE Coordinator and the MCCC IND Coordinator to determine if FDA submission is needed

REPORTING TO NOVARTIS

Contact Novartis within 24 hours: [contact](see appendix V)

Reporting

For patients who sign the main study ICF, SAE collection starts at time of main study informed consent whether the patient is a screen failure or not.

To ensure patient safety, every SAE, regardless of suspected causality, occurring after the patient has provided informed consent and until at least 30 days after the patient has stopped study treatment must be reported to Novartis within 24 hours of learning of its occurrence.

Any SAEs experienced after this 30 days period (or 5 half-lives) whichever is longer) should only be reported to Novartis if the investigator suspects a causal relationship to the study treatment. Recurrent episodes, complications, or progression of the initial SAE must be reported as follow-up to the original episode within 24 hours of the investigator receiving the follow-up information. An SAE occurring at a different time interval or otherwise considered completely unrelated to a previously reported one should be reported separately as a new event.

Information about all SAEs is collected and recorded on the Serious Adverse Event Report Form, such as a FDA MedWatch Form; all applicable sections of the form must be completed in order to provide a clinically thorough report. The investigator must assess and record the relationship of each SAE to each specific study treatment (if there is more than one study treatment), complete the SAE Report Form in English, and send the completed, signed form by fax within 24 hours to the oncology Novartis Drug Safety and Epidemiology (DS&E) department at Fax Number: [REDACTED].

The telephone and telefax number of the contact persons in the local department of Drug Safety and Epidemiology (DS&E), specific to the site, are listed as an appendix to the Site Agreement. The original copy of the SAE Report Form and the fax confirmation sheet must be kept with the case report form documentation at the study site.

Follow-up information is sent to the same contact(s) to whom the original SAE Report Form was sent, using a new SAE Report Form stating that this is a follow-up to the previously reported SAE and giving the date of the original report. Each re-occurrence, complication, or progression of the original event should be reported as a follow-up to

that event regardless of when it occurs. The follow-up information should describe whether the event has resolved or continues, if and how it was treated, whether the blind was broken or not, and whether the patient continued or withdrew from study participation.

If the SAE is not previously documented in the Investigator’s Brochure (new occurrence) and is thought to be related to the Novartis study treatment, an oncology Novartis Drug Safety and Epidemiology (DS&E) department associate may urgently require further information from the investigator for Health Authority reporting. Novartis may need to issue an Investigator Notification (IN), to inform all investigators involved in any study with the same drug that this SAE has been reported. Suspected Unexpected Serious Adverse Reactions (SUSARs) will be collected and reported to the competent authorities and relevant ethics committees in accordance with Directive 2001/20/EC or as per national regulatory requirements in participating countries.

Pregnancy reporting

To ensure patient safety, each pregnancy occurring while the patient is on study treatment must be reported to Novartis within 24 hours of learning of its occurrence. The pregnancy should be followed up to determine outcome, including spontaneous or voluntary termination, details of the birth, and the presence or absence of any birth defects, congenital abnormalities, or maternal and/or newborn complications.

Pregnancy should be recorded on a Clinical Trial Pregnancy Form and reported by the investigator to the oncology Novartis Drug Safety and Epidemiology Department (DS&E). Pregnancy follow-up should be recorded on the same form and should include an assessment of the possible relationship to midostaurin. Any SAE experienced during pregnancy must be reported on the SAE Report Form.

Pregnancy outcomes must be collected for the female partners of any males who took study treatment in this study. Consent to report information regarding these pregnancy outcomes should be obtained from the mother.

1. Use paper *Adverse Event Expedited Report – Single Agent or Multiple Agents* report available from the CTEP Home Page at http://ctep.cancer.gov/protocolDevelopment/electronic_applications/docs/34-adeersv4_mat.pdf . AdEERs Templates. Submit to Novartis (see fax sheet included in the forms packet) (see Appendix V).

Provide copies, along with the UPIRTSO cover sheet, by fax [REDACTED] to the MCCC Regulatory Affairs Unit (RAU) Risk Information Specialist who will determine and complete IRB reporting. The RAU will submit to the MCCC SAE Coordinator and the MCCC IND Coordinator to determine if FDA submission is needed.

10.5 Other Required Reporting

10.51 Adverse events to be graded at each evaluation and pretreatment symptoms/conditions to be evaluated at baseline per the CTCAE v4.0 grading unless otherwise stated in the table below:

System Organ Class (SOC)	Adverse event/Symptoms	Baseline	Each evaluation
--------------------------	------------------------	----------	-----------------

Investigations	Electrocardiogram QT corrected interval prolonged	X	X
	Blood bilirubin increased	X	X
	Alanine aminotransferase increased	X	X
	Aspartate aminotransferase increased	X	X
	Lipase increased	X	X
Skin and subcutaneous tissue disorders	Rash maculo-papular	X	X

10.52 Submit via appropriate MCCC Case Report Forms (i.e., paper or electronic, as applicable) the following AEs experienced by a patient and not specified in Section 10.51:

10.521 Grade 2 AEs deemed *possibly, probably, or definitely* related to the study treatment or procedure.

10.522 Grade 3 and 4 AEs regardless of attribution to the study treatment or procedure.

10.523 Grade 5 AEs (Deaths)

10.5231 Any death within 30 days of the patient's last study treatment or procedure regardless of attribution to the study treatment or procedure.

10.5232 Any death more than 30 days after the patient's last study treatment or procedure that is felt to be at least possibly treatment related must also be submitted as a Grade 5 AE, with a CTCAE type and attribution assigned.

10.53 Refer to the instructions in the Forms Packet (or electronic data entry screens, as applicable) regarding the submission of late occurring AEs following completion of the Active Monitoring Phase (i.e., compliance with Test Schedule in Section 4.0).

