Overall, approximately 1687 subjects have received midostaurin including ~650 patients with AML / MDS. In AML patients, doses of up to 600 mg per day have been given, but the 50 mg twice daily dose is recommended based upon reaching the IC50 and showing acceptable tolerability. Safety data in AML are based upon three studies: monotherapy in FLT3 mutated patients (2104 Core; N=20), monotherapy in relapsed AML or ineligible for chemotherapy (2104E1; N=95) and front-line combination therapy with daunorubicin and cytarabine (2106; N=69). (Stone 2005, Fischer 2010, Stone 2012). Data from the maintenance phase of the Phase III (2301, CALGB 10603 Ratify) study would also be very informative but the ongoing trial remains blinded at this time. Single agent safety data from 2104E1 will be discussed.

In study 2104E1, patients were randomized to receive midostaurin at doses of 50 mg b.i.d. or 100 mg b.i.d. Of the patients enrolled, 73% were relapsed/refractory and 61% were greater than 60 years of age. Six patients had previously undergone HSCT. Midostaurin was generally well tolerated at both dose levels. All 95 patients experienced at least one AE regardless of relationship to study drug. The most frequent events were grades 1 or 2 nausea (61%; Grade 3 was 1%), vomiting (49%; Grade 3 was 1%), diarrhea (44%; Grade 3 or 4 was 5%), fatigue (38%; Grade 3 was 3%), pyrexia (35%; Grade 3 was 7%) and dyspnea (29%; Grade 3 or 4 9%). The most commonly reported grade 3 / 4 AEs were febrile neutropenia (21%), thrombocytopenia (19%), neutropenia (12%), anemia (13%) and pneumonia (12%). [Inv Brochure ed 16, Table 6-20] The decreases observed in the hematology parameters were as expected for this patient population. Only one patient discontinued treatment due to a hematologic

abnormality (grade 3 febrile neutropenia). The majority of new or worsened biochemistry abnormalities were of CTC grade 1-2. There were grade 3 or 4 abnormalities in AST/ALT in 13% patients (2 were Grade 4, both receiving 100 mg b.i.d.), amylase 7% and albumin 5%. The full table of newly occurring or worsening hematology and chemistry abnormalities is shown in the Investigators Brochure.

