Overall, AEs suspected to be related to midostaurin treatment were mostly Grade 1 and 2 gastrointestinal events requiring little or no intervention. These were considered related to midostaurin, as the frequency increased at higher dose levels. At the 100 mg twice daily dose in AML patients with chemotherapy, patients discontinued treatment more frequently due to nausea and vomiting despite addition of antiemetic therapy which contributed to selection of a 50 mg twice daily dose which was found to be well tolerated. In addition to prophylactic anti-emetics, administering the doses with meals can reduce gastrointestinal AEs. These AEs are most common in the early cycles of administration. In the ongoing ASM/MCL studies, patients are tolerating the 100 mg twice daily dose for up to 4 years; however, prophylactic anti-emetics are given to all patients.

Overview of decitabine

Decitabine, one of the hypomethylating agents, is FDA approved for the management of myelodysplastic syndrome. In Europe decitabine is also approved for AML in elderly patients 65 or older. It has been also found to be effective in patients with AML. For elderly AML patients unfit for chemotherapy, hypomethylating agents are the cornerstone for treatment due to its low toxicity and safe profile. In a phase III study (Kantarjian 2012), decitabine given 20 mg/m² as 1-hour intravenous infusion daily for five days every four weeks improved response rates compared with standard therapies without major differences in safety. CR was achieved in 18% with decitabine versus 8% in the other arm.

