- 16.325 Adverse Events: All eligible patients that have initiated treatment will be considered evaluable for assessing adverse event rate(s). The maximum grade for each type of adverse event will be recorded for each patient, and frequency tables will be reviewed to determine patterns. Additionally, the relationship of the adverse event(s) to the study treatment will be taken into consideration.

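### Outside six listed terms, routine reporting omits non-serious Grade 1 and non-serious unrelated Grade 2 events, yet 16.325 tabulates maximum grade with no cut-off, so low-grade nausea, vomiting and diarrhea will be undercounted

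*Combined protocol and SAP*

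**What the plan says.** Section 10.51 is introduced as "Adverse events to be graded at each evaluation and pretreatment symptoms/conditions to be evaluated at baseline". Its table has six rows: QTc prolongation, bilirubin, ALT, AST, lipase and maculo-papular rash.

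Section 10.52 covers "the following AEs experienced by a patient and not specified in Section 10.51". For these it asks for "Grade 2 AEs deemed *possibly, probably, or definitely* related to the study treatment or procedure" (10.521), "Grade 3 and 4 AEs regardless of attribution to the study treatment or procedure" (10.522), and deaths, subject to a 30-day rule (10.523). Grade 1 does not appear.

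A second route exists. Section 10.41 requires expedited reports of serious events, including low-grade events that lead to hospitalization of 24 hours or more. Section 10.11 adds: "All AEs reported via expedited mechanisms must also be reported via the routine data reporting mechanisms defined by the protocol".

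The analysis in 16.325 reads: "The maximum grade for each type of adverse event will be recorded for each patient, and frequency tables will be reviewed to determine patterns". It adds that relationship to treatment will be considered. It does not mention the collection rules of 10.51 and 10.52.

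On what to expect, Section 1.2 says that "AEs suspected to be related to midostaurin treatment were mostly Grade 1 and 2 gastrointestinal events requiring little or no intervention". It also lists nausea, vomiting and diarrhea among the most common drug-related toxicities in the pooled analysis.

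**The concern.** A table of maximum grade per patient can be read at face value only down to the lowest grade that is collected. For a term outside 10.51, a patient whose worst nausea was non-serious Grade 1 has no record and cannot be told apart from a patient with none. In the same table, Grade 2 counts have passed an attribution filter and Grade 3 and 4 counts have not.

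The cut falls where the protocol expects midostaurin's related toxicity to lie. The trial has one arm, so its safety tables will be set beside outside figures. The nearest in the document are the monotherapy rates in Section 1.2, from a study whose events are introduced as counted whatever their relation to the drug. Lower rates here could then reflect the collection rule rather than better tolerability. Safety is a stated secondary goal (2.24), and 16.5 plans public reporting of the secondary endpoints.

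Baseline has the same gap. Section 6.8 points to 10.5 for the symptoms to be graded at entry, so nausea present before treatment is not a required baseline item, although 10.521 depends on a judgment of relatedness.

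**Working it through.** The plan gives no figure to reproduce here. The check is a reading of the rules, followed by an illustration of size.

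**Step 1: what reaches the routine data.**

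| Event | Six terms in 10.51 | All other terms |
|---|---|---|
| Grade 1, non-serious | graded at each evaluation | not requested |
| Grade 2, non-serious, at least possibly related | graded at each evaluation | 10.521 |
| Grade 2, non-serious, judged unrelated | graded at each evaluation | not requested |
| Grade 1 or 2, serious or hospitalized | graded at each evaluation | via 10.41 and 10.11 |
| Grade 3 or 4 | graded at each evaluation | 10.522, any attribution |

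Two cells are empty, both in the right-hand column. Nausea, vomiting and diarrhea belong to that column. Section 16.325 states no cut-off that would keep those cells out of its tables. The omission can lower a count but never raise it.

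**Step 2: which cell matters for gastrointestinal events.** Section 1.2 says these events were considered related to midostaurin, so most at Grade 2 should meet 10.521. The loss is chiefly non-serious Grade 1.

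**Step 3: illustration of size.** Inputs:
- N = 24 evaluable patients (16.22). Section 16.325 counts eligible patients who started treatment, so the 2 extra patients allowed for ineligibility, cancellation and the like are left out.
- r = Grade 1 or 2 rate in the monotherapy study of 95 patients (Section 1.2): nausea 0.61, vomiting 0.49, diarrhea 0.44.
- s = share of those patients whose worst grade is 1. The document does not give it. **Assumption:** 0.25, 0.50 and 0.75. Every Grade 2 event is taken as called related, and every Grade 1 event as non-serious.

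Patients missed = N × r × s. Recorded Grade 1–2 rate = r × (1 − s).

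| Term | N × r | Missed at s = 0.25 / 0.50 / 0.75 | Recorded rate at s = 0.25 to 0.75 |
|---|---|---|---|
| Nausea | 24 × 0.61 = 14.6 | 3.7 / 7.3 / 11.0 | 46% to 15% |
| Vomiting | 24 × 0.49 = 11.8 | 2.9 / 5.9 / 8.8 | 37% to 12% |
| Diarrhea | 24 × 0.44 = 10.6 | 2.6 / 5.3 / 7.9 | 33% to 11% |

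Over the whole range of s from 0 to 1, the number missed runs from 0 to 14.6, 11.8 and 10.6.

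**Step 4: what is untouched.** The primary endpoint is CR or CRi with a rule of 5 or more successes in 24 (16.211). The stopping rule in 16.42 counts related non-hematologic events of Grade 4 or higher, which 10.522 and 10.523 collect.

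**The case against.** The strongest reply is that tiered reporting is a legitimate, plainly stated rule that nothing else in the protocol contradicts. That is right: the tiering itself is not an error. What is missing is any link between the tier and the tables.

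Several stronger readings are tempting and should be resisted.

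- *Grade 1 events are never collected, and Grade 2 events only if related.* This is too absolute. Serious or hospitalized low-grade events are reported under 10.41 whatever their attribution, and 10.11 brings them into the routine data.
- *Section 16.325 presents its tables as complete.* It does not. It is silent on completeness, and that silence is the defect.
- *Grade 2 gastrointestinal toxicity is lost through the attribution filter.* This is weak for these terms. Section 1.2 regards them as drug-related. The table in 8.2, under which persistent Grade 2 nausea or vomiting leads to omitted midostaurin doses, applies to events at least possibly related, the same threshold as 10.521. Events acted on there are reportable.
- *Recorded rates will be well below the true ones by a known amount.* Section 1.2 does not separate Grade 1 from Grade 2. Its rates come from a study of 50 or 100 mg twice daily in which 73% of patients were relapsed or refractory. This trial starts at 50 mg twice daily on days 8–21, and 15.193 advises antiemetic premedication. Section 1.2 says that lower doses, antiemetics and food go with fewer such events.

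One could add that the lost events needed little or no intervention. That limits their clinical weight but not the undercount, and they remain part of the profile that goal 2.24 sets out to describe.

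**Conclusion.** The point stands in limited form. Outside the six terms in 10.51, routine reporting omits non-serious Grade 1 events and non-serious Grade 2 events judged unrelated, and 16.325 tabulates maximum grade without acknowledging it. Low-grade nausea, vomiting and diarrhea will be undercounted, chiefly at Grade 1.

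The direction follows from the text alone. The size does not: about 4 to 11 of 24 patients for nausea is an illustration that rests on an assumed Grade 1 share of 25% to 75% and on a monotherapy rate that may not carry over to this regimen.

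The consequence is confined to the descriptive secondary safety goal. The primary endpoint, the decision rule and the Grade 4+ stopping rule are unaffected. The change is worth making because it is cheap and decides what the safety tables can show.

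**What to change.** 1. Add nausea, vomiting and diarrhea to the 10.51 table, at baseline and at each evaluation. Adverse-event assessment is already scheduled before treatment, on Day 1 of each cycle and at end of treatment (Section 4.0). The cost is three more rows of data entry per evaluation. This must be in place before the data are collected; it cannot be recovered in analysis.
2. In 16.325, tie the tables to what is collected. For the 10.51 terms, report all grades regardless of attribution. For all other terms, report Grade 3 and above regardless of attribution (deaths as defined in 10.523), and Grade 2 only in the table of at least possibly related events. State the threshold with the tables, and note that some serious low-grade events arrive by the expedited route and do not support a rate. This costs wording only.

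The 10.51 terms must be exempt from the Grade 3 cut-off. A blanket cut-off would discard valid all-grade data on QTc, bilirubin, ALT, AST, lipase and rash.
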